### **4.2.3 Rationale for Endpoints**

#### **4.2.3.1 Efficacy Endpoints**

The primary endpoint will be objective response rate (ORR), while the secondary endpoints will be progression-free survival (PFS) and overall survival (OS). The rationale for using ORR as the primary endpoint is that this trial is a single-arm trial; assessing ORR will allow us to attribute the effect of treatment directly to pembrolizumab, not to the natural history of NSCLC.

Since ORR cannot comprehensively measure drug activity, PFS and OS will be used as secondary endpoints. This will allow us to account for deaths that are unrelated to cancer and to the effects of pembrolizumab. PFS is an acceptable measure of clinical benefit for a Phase 2 trial that demonstrates superiority of a new antineoplastic therapy, especially if the magnitude of effect is large and the therapy has an acceptable risk-benefit profile. Furthermore, it is an endorsed regulatory endpoint for 1L NSCLC trials with recent FDA and EMA approvals including the EGFR inhibitors afatinib and erlotinib. PFS will be assessed by RECIST 1.1 by an independent central radiologists' review. Although PFS assesses how long a patient is on trial without progressing, since we have seen that EGFR mutant patients have

a high response rate, we will also collect OS data to determine if pembrolizumab is comparable to TKI therapy or standard of care chemotherapy. Further, OS is a standard assessment of clinical benefit in subjects with advanced or metastatic NSCLC. OS will be assessed by RECIST 1.1 criteria by independent central radiology review.

## 5.0 METHODOLOGY

### 5.1 Entry Criteria

#### 5.1.1 Diagnosis/Condition for Entry into the Trial

Refer to sections 5.1.2 and 5.1.3 of the protocol for more detailed information.

#### 5.1.2 Subject Inclusion Criteria

In order to be eligible for participation in this trial, the subject must:

1. Ability to understand the purpose and risks of the study and provide signed and dated informed consent and authorization to use protected health information (PHI).
2. Be  $\geq 18$  years of age on day of signing informed consent.
3. Have a life expectancy of at least 3 months.
4. Have a histologically or cytologically confirmed diagnosis of Stage IIIB or IV non-small cell lung cancer (NSCLC) and have at least one measurable lesion as defined by modified RECIST 1.1. The target lesion(s) should also have bi-dimensional measurability for RECIST 1.1 evaluation on study.
5. Have an EGFR mutation (sensitizing or non-sensitizing) as determined by any CLIA certified laboratory.
6. Have a performance status of 0 or 1 on the ECOG Performance Scale.
7. Have adequate organ function

Table 1 Adequate Organ Function Laboratory Values

System	Laboratory Value
Hematological	
Absolute neutrophil count (ANC)	$\geq 1,500$ /mcL
Platelets	$\geq 100,000$ / mcL
Hemoglobin	$\geq 9$ g/dL or $\geq 5.6$ mmol/L without transfusion or EPO dependency (within 7 days of assessment)

Renal	
Serum creatinine OR Measured or calculated a creatinine clearance (GFR can also be used in place of creatinine or CrCl)	≤1.5 X upper limit of normal (ULN) OR ≥60 mL/min for subject with creatinine levels > 1.5 X institutional ULN
Hepatic	
Serum total bilirubin	≤ 1.5 X ULN OR
	Direct bilirubin ≤ ULN for subjects with total bilirubin levels > 1.5 ULN
AST (SGOT) and ALT (SGPT)	≤ 2.5 X ULN OR ≤ 5 X ULN for subjects with liver metastases
Albumin	≥2.5 mg/dL
Coagulation	
International Normalized Ratio (INR) or Prothrombin Time (PT)	≤1.5 X ULN unless subject is receiving anticoagulant therapy as long as PT or PTT is within therapeutic range of intended use of anticoagulants
Activated Partial Thromboplastin Time (aPTT)	≤1.5 X ULN unless subject is receiving anticoagulant therapy as long as PT or PTT is within therapeutic range of intended use of anticoagulants
a Creatinine clearance should be calculated using the standard Cockcroft and Gault equation.	

8. Have provided tissue for PD-L1 biomarker analysis from either a newly obtained or archival formalin fixed tumor tissue from a biopsy of a tumor lesion not previously irradiated for analysis of PD-L1 expression. The tissue sample must be received and evaluated by the study site prior to start of treatment. Fine needle aspirates are not acceptable. Needle or excisional biopsies, or resected tissue is required.
9. Have a PD-L1 positive (either strongly or weakly) tumor as determined by the IHC 22C3 pharmDx test at the study site. If a patient's initial tumor specimen is not classified as PD-L1 positive a newly obtained specimen (different from the sample previously submitted) may be submitted for testing. If the newer specimen is classified as PD-L1 positive by the study site, the patient meets this eligibility criterion. Positivity can either be determined at the central laboratory or at any CLIA-certified laboratory using the 22C3 antibody.
10. Have resolution of toxic effect(s) of the most recent prior chemotherapy to Grade 1 or less (except alopecia). If subject received major surgery or radiation therapy of > 30 Gy, they must have recovered from the toxicity and/or complications from the intervention.

11. Female subject of childbearing potential has a negative urine or serum pregnancy test. If the urine test is positive or cannot be confirmed as negative, a serum pregnancy test will be required. The serum pregnancy test must be negative for the subject to be eligible.
12. Female subjects may be enrolled in the trial if they are:
  - of non-childbearing potential which is defined as a woman who is postmenarcheal, has not reached a postmenopausal state (at least 12 continuous months of amenorrhea with no identified cause other than menopause), and has not undergone surgical sterilization (removal of ovaries and/or uterus).
  - of childbearing potential who are willing to use either 2 adequate barrier methods or a barrier method plus a hormonal method of contraception to prevent pregnancy, or to abstain from heterosexual activity throughout the trial, starting with the screening visit (Visit 1) through 120 days after the last dose of pembrolizumab.
13. Male subjects should agree to use an adequate method of contraception starting with the first dose of study therapy through 120 days after the last dose of study therapy.

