### 5.5.2 Contraception

Pembrolizumab may have adverse effects on a fetus in utero. Furthermore, it is not known if pembrolizumab has transient adverse effects on the composition of sperm. Non-pregnant, non-breast-feeding women may be enrolled if they are willing to use 2 methods of birth control or are considered highly unlikely to conceive. Highly unlikely to conceive is defined as 1) surgically sterilized, or 2) postmenopausal (a woman who is  $\geq 45$  years of age and has not had menses for greater than 1 year will be considered postmenopausal), or 3) not heterosexually active for the duration of the study. The two birth control methods can be either two barrier methods or a barrier method plus a hormonal method to prevent pregnancy. Subjects should start using birth control from study Visit 1 throughout the study period up to 120 days after the last dose of study therapy.

The following are considered adequate barrier methods of contraception: diaphragm, condom (by the partner), copper intrauterine device, sponge, or spermicide. Appropriate hormonal contraceptives will include any registered and marketed contraceptive agent that contains an estrogen and/or a progestational agent (including oral, subcutaneous, intrauterine, or intramuscular agents).

Subjects should be informed that taking the study medication may involve unknown risks to the fetus (unborn baby) if pregnancy were to occur during the study. In order to participate in the study they must adhere to the contraception requirement (described above) for the duration of the study and during the follow-up period defined in section 7.2.2-Reporting of Pregnancy and Lactation to UCLA DSMB. If there is any question that a subject will not reliably comply with the requirements for contraception, that subject should not be entered into the study.

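### Inclusion criterion 12, first bullet, is inverted: its definition of non-childbearing potential describes a woman who can conceive, and it contradicts section 5.5.2 (minor)

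*Combined protocol and SAP*

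**What the plan says.** Criterion 12 (section 5.1.2) gives two routes by which a woman may enroll.

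- First bullet: women "of non-childbearing potential which is defined as a woman who is postmenarcheal, has not reached a postmenopausal state", the latter explained as "at least 12 continuous months of amenorrhea with no identified cause other than menopause", "and has not undergone surgical sterilization (removal of ovaries and/or uterus"). No contraception undertaking is attached.
- Second bullet: women "of childbearing potential who are willing to use either 2 adequate barrier methods", or one barrier method plus a hormonal one, "or to abstain from heterosexual activity throughout the trial". The undertaking runs from screening until 120 days past the final dose. Criterion 12 does not separately define childbearing potential.

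Section 5.5.2 lets non-pregnant, non-breast-feeding women enroll if they accept two methods of birth control or are unlikely to conceive: "Highly unlikely to conceive is defined as 1) surgically sterilized, or 2) postmenopausal", with a third limb, "3) not heterosexually active for the duration of the study". It counts as postmenopausal a woman aged 45 or older who "has not had menses for greater than 1 year will be considered postmenopausal".

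Criterion 11 and the footnote to Table 5 (section 7.1.3) tie the pregnancy test to childbearing potential. Section 7.1.5.1.1 ties its pre-dose urine test to reproductive potential, a different term.

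**The concern.** All three features in the first bullet (has reached menarche, has not reached menopause, has not been sterilized) are those of a woman who can become pregnant. The text therefore attaches the definition of childbearing potential to the opposite label.

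This is an operative eligibility and safety rule for a drug that section 5.5.2 says could harm a fetus. If applied as written, the bullet would do two things:

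- It would admit a fertile woman without asking her for contraception.
- It would fail to admit the women for whom that bullet was evidently written.

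It is also the only definition attached to a term that criterion 11 and the Table 5 footnote rely on to decide who is tested for pregnancy.

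**Working it through.** The plan gives no figure to reproduce, so the check is a comparison of the two texts. The first-bullet sentence is complete and grammatical, with no gap or black-out, so the inversion does not look like a reading artifact.

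**Step 1: write both rules with the same symbols.** Let P = postmenopausal, S = surgically sterilized, A = heterosexually active. Entry age is 18 or over; assume every woman has reached menarche.

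- Criterion 12, first bullet: not P and not S.
- Section 5.5.2, exempt from contraception: P or S or not A.

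On P and S alone, *not P and not S* is the exact negation of *P or S*. The contradiction needs no further assumption about the second bullet, only that P and S mean the same in both sections.

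**Step 2: what follows for each woman.** This depends on what childbearing potential means in the second bullet.

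*Reading (a): everyone not in the first bullet.* For heterosexually active women:

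| Profile | Criterion 12 asks for a method? | Section 5.5.2 asks for a method? | Agree? |
|---|---|---|---|
| not P, not S | No (first bullet) | Yes | No; criterion 12 too lax |
| not P, S | Yes (second bullet) | No | No; criterion 12 too strict |
| P, not S | Yes (second bullet) | No | No; criterion 12 too strict |
| P, S | Yes (second bullet) | No | No; criterion 12 too strict |

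That is 4 of 4 in conflict, 1 in the unsafe direction and 3 over-cautious. For women who abstain, neither text asks for a method, so 0 of 4 conflict. The total is 4 + 0 = 4 of 8.

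*Reading (b): the ordinary meaning.* A fertile woman then fits both bullets and can still enter by the first. A postmenopausal or sterilized woman fits neither. The tally in the table does not apply, because criterion 12 no longer says what is asked of three of the four groups.

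Under both readings, a fertile woman meets a bullet with no undertaking. A heterosexually active postmenopausal or sterilized woman who uses no contraception is not admitted.

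**Step 3: does swapping the labels settle it?** With the first bullet as *P or S* and the second as *not P and not S* (abstinence accepted), a method is needed only when not P, not S and A. That equals section 5.5.2, so 0 of 8 conflict, provided P, S and abstinence mean the same in both places. At present they do not:

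- **Postmenopausal.** Criterion 12 has no age limit; section 5.5.2 requires age 45 or older. Criterion 12 also rules out other causes of amenorrhea, which section 5.5.2 does not.
- **Sterilized.** Criterion 12 limits this to removal of ovaries and/or uterus; section 5.5.2 gives no limit. Take a premenopausal, active woman sterilized by another procedure. Today she meets the first bullet and is exempt under section 5.5.2, so the texts agree by accident. After a bare label swap she would need a method under criterion 12 and none under section 5.5.2.
- **Abstinence.** The second bullet runs to 120 days past the final dose; the third limb of section 5.5.2 covers the study's duration.

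So the count of 4 requires reading (a) and one shared meaning of P and S. The count of 0 after rewording requires the definitions to be aligned as well.

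**The case against.** The best reply is that this is a slip whose intended meaning any investigator would see, and that the rules are cumulative. Criterion 12 only permits enrollment; it does not cancel anything else. Section 5.5.2 makes adherence to its contraception requirement a condition of taking part and bars women whose compliance is in doubt. Section 7.1.5.1.1 requires a urine test within 72 hours before the first dose, under a term that the faulty definition does not touch. The flow chart lists a screening pregnancy test. Exclusion 19 bars women who are pregnant or expect to conceive. Under section 8.2.1 a compliance officer checks eligibility before enrollment.

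Most of that stands, and it fixes the severity as minor. A reader might infer that fertile women could be treated untested or with no contraception requirement. The documents do not support that, because the rules just listed apply regardless of criterion 12. A reader might also take 4 of 4 as a measured size. It is not: it holds only under reading (a) with shared definitions, and the documents give no frequencies for the profiles.

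What does not stand is the idea that the safeguards cure the criterion. They sit elsewhere and leave two sections giving opposite answers. The eligibility check is the weakest of them, because an officer checks against the written criteria. Section 8.1 also sends eligibility deviations to a DSMB member for approval, so a properly enrolled postmenopausal woman using no contraception could be queried as a deviation.

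**Conclusion.** The first bullet of criterion 12 is inverted and contradicts section 5.5.2. On menopause and sterilization, one is the logical negation of the other wherever the two sections use those words alike. That conclusion rests on the text alone and is firm.

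The severity is minor. Other rules still bind a fertile woman, and the error does not touch the sample size, the power or the response-rate analysis. The documents do not say how many women are affected, and they give no ground for saying that anyone was wrongly enrolled. The profile counts (4 of 8 now, 0 of 8 after a fully aligned rewording) illustrate the conflict under the assumptions stated in the working; they do not measure its size.

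**What to change.** Amend criterion 12 and section 5.5.2 together:

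1. First bullet: define non-childbearing potential as postmenopausal or surgically sterilized.
2. Second bullet: attach the three existing features (past menarche, not postmenopausal, not sterilized) to childbearing potential, and keep the contraception and abstinence options.
3. Use one definition of postmenopausal in both sections, deciding whether the age limit of 45 applies and whether other causes of amenorrhea must be ruled out.
4. Use one definition of surgical sterilization in both sections: either removal of ovaries and/or uterus, or any sterilizing procedure.
5. Use one abstinence period in both sections, running to 120 days past the final dose.

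Criterion 11 and the Table 5 footnote then work without further change. The cost is a few lines in a text amendment. A look back at women already screened is optional. Nothing changes in design, sample size or analysis.

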### **5.1.3 Subject Exclusion Criteria**

The subject must be excluded from participating in the trial if the subject:

1. Has received prior therapy with an EGFR tyrosine kinase inhibitor (such as erlotinib, gefitinib, afatinib, rociletinib, or AZD9291) for NSCLC.
2. Is currently participating or has participated in a study of an investigational agent or using an investigational device within 30 days of the first dose of trial treatment. The 30 day window should be applied to the last dose of an antineoplastic investigational agent or last use of an investigational device with antineoplastic intent.
3. Is receiving systemic steroid therapy within three days prior to the first dose of trial treatment or receiving any other form of immunosuppressive medication (corticosteroid use on study for management of ECIs is allowed).
4. Is expected to require any other form of systemic or localized antineoplastic therapy while on trial (including maintenance therapy with another agent for NSCLC or radiation therapy).
5. Has received prior systemic cytotoxic chemotherapy, antineoplastic biological therapy (e.g., cetuximab), major surgery within 3 weeks of the first dose of trial treatment; received thoracic radiation therapy of > 30 Gy within 6 months of the first dose of trial treatment.
6. Has received prior therapy with an anti-PD-1, anti-PD-L1, anti-PD-L2, anti-CD137, or anti-Cytotoxic T-lymphocyte-associated antigen-4 (CTLA-4) antibody (including ipilimumab or any other antibody or drug specifically targeting T-cell co-stimulation or checkpoint pathways). Has participated in another pembrolizumab clinical trial.

7. Has a known history of prior malignancy that in the opinion of the investigator interferes with the ability to interpret the radiographic results (e.g. a second active malignancy with some lesions being of uncertain origin).
8. Subjects with central nervous system (CNS) metastases and/or carcinomatous meningitis may participate provided they are clinically stable, and are using no steroids for at least seven days prior to study medication.
9. Has an active autoimmune disease, or a documented history of autoimmune disease that required systemic steroids or immunosuppressive agents. Subjects with vitiligo or resolved childhood asthma/atopy would be exception to this rule. Subjects that require inhaled steroid or local steroid injections will not be excluded from the study. Subjects with hypothyroidism who are stable on hormone replacement will not be excluded from the study.
10. Has had an allogeneic tissue/solid organ transplant.
11. Has interstitial lung disease or a history of pneumonitis that required oral or intravenous glucocorticoids to assist with management. Lymphangitic spread of the NSCLC is not exclusionary.
12. Has received or will receive a live vaccine within 30 days prior to the first administration of study medication. Seasonal flu vaccines that do not contain live virus are permitted.
13. Has an active infection requiring intravenous systemic therapy.
14. Has known history of Human Immunodeficiency Virus (HIV) (HIV 1/2 antibodies).
15. Has known active Hepatitis B or C. Active Hepatitis B is defined as a known positive HBsAg result. Active Hepatitis C is defined by a known positive Hep C Ab result and known quantitative HCV RNA results greater than the lower limits of detection of the assay.
16. Has a history or current evidence of any condition, therapy, or laboratory abnormality that might confound the results of the trial, interfere with the subject's participation for the full duration of the trial, or is not in the best interest of the subject to participate, in the opinion of the treating Investigator.
17. Has known psychiatric or substance abuse disorders that would interfere with cooperation with the requirements of the trial.
18. Is, at the time of signing informed consent, a regular user (including "recreational use") of any illicit drugs or had a recent history (within the last year) of substance abuse (including alcohol).

19. Is pregnant or breastfeeding, or expecting to conceive or father children within the projected duration of the trial, starting with the screening visit (Visit 1) through 120 days after the last dose of pembrolizumab.

## 5.2 Trial Treatments

The treatment to be used in this trial is outlined below in Table 2

Table 2 Trial Treatment

Drug	Dose/Potency	Dose Frequency	Route of Administration	Regimen/Treatment Period	Use
Pembrolizumab	200 mg	Q3W	IV infusion	Day 1 of each 3 week cycle	Experimental

Trial treatment should begin on the day of randomization or as close as possible to the date on which treatment is allocated/assigned.

### 5.2.1 Dose Selection/Modification

#### 5.2.1.1 Dose Selection

The rationale for selection of doses to be used in this trial is provided in Section 4.0 – Background and Rationale. Details on preparation and administration of pembrolizumab (MK-3475) are provided in the Pharmacy Manual.

#### 5.2.1.2 Dose Modification

Adverse events (both non-serious and serious) associated with pembrolizumab exposure may represent an immunologic etiology. These adverse events may occur shortly after the first dose or several months after the last dose of treatment. Pembrolizumab must be withheld for drug-related toxicities and severe or life-threatening AEs as per Table 3 below. See Section 5.6.1 for supportive care guidelines, including use of corticosteroids.

Table 3

Dose Modification Guidelines for Drug-Related Adverse Events

General instructions:

 
1. Corticosteroid taper should be initiated upon AE improving to Grade 1 or less and continue to taper over at least 4 weeks.
 
2. For situations where pembrolizumab has been withheld, pembrolizumab can be resumed after AE has been reduced to Grade 1 or 0 and corticosteroid has been tapered. Pembrolizumab should be permanently discontinued if AE does not resolve within 12 weeks of last dose or corticosteroids cannot be reduced to <math>\leq 10</math> mg prednisone or equivalent per day within 12 weeks.
 
3. For severe and life-threatening irAEs, IV corticosteroid should be initiated first followed by oral steroid. Other immunosuppressive treatment should be initiated if irAEs cannot be controlled by corticosteroids.
 

Immune-related AEs	Toxicity grade or conditions (CTCAEv4.0)	Action taken to pembrolizumab	irAE management with corticosteroid and/or other therapies	Monitor and follow-up
Pneumonitis	Grade 2	Withhold	
 
Administer corticosteroids (initial dose of 1-2 mg/kg prednisone or equivalent) followed by taper
 
	
 
Monitor participants for signs and symptoms of pneumonitis
 
Evaluate participants with suspected pneumonitis with radiographic imaging and initiate corticosteroid treatment
 
Add prophylactic antibiotics for opportunistic infections
 

	Grade 3 or 4, or recurrent Grade 2	Permanently discontinue		
Diarrhea / Colitis	Grade 2 or 3	Withhold	
 
Administer corticosteroids (initial dose of 1-2 mg/kg prednisone or equivalent) followed by taper
 
	
 
Monitor participants for signs and symptoms of enterocolitis (ie, diarrhea, abdominal pain, blood or mucus in stool with or without fever) and of bowel perforation (ie, peritoneal signs and ileus).
 
Participants with <math>\geq</math> Grade 2 diarrhea suspecting colitis should consider GI consultation and performing endoscopy to rule out colitis.
 
Participants with diarrhea/colitis should be advised to drink liberal quantities of clear fluids. If sufficient oral fluid intake is not feasible, fluid and electrolytes should be substituted via IV infusion.
 

	Grade 4	Permanently discontinue		

AST / ALT elevation or Increased bilirubin	Grade 2	Withhold	
 
Administer corticosteroids (initial dose of 0.5- 1 mg/kg prednisone or equivalent) followed by taper
 
	
 
Monitor with liver function tests (consider weekly or more frequently until liver enzyme value returned to baseline or is stable)
 

	Grade 3 or 4	Permanently discontinue	
 
Administer corticosteroids (initial dose of 1-2 mg/kg prednisone or equivalent) followed by taper
 
	
Type 1 diabetes mellitus (T1DM) or Hyperglycemia	Newly onset T1DM or Grade 3 or 4 hyperglycemia associated with evidence of $\beta$ -cell failure	Withhold	
 
Initiate insulin replacement therapy for participants with T1DM
 
Administer anti-hyperglycemic in participants with hyperglycemia
 
	
 
Monitor participants for hyperglycemia or other signs and symptoms of diabetes.
 

Hypophysitis	Grade 2	Withhold	
 
Administer corticosteroids and initiate hormonal replacements as clinically indicated.
 
	
 
Monitor for signs and symptoms of hypophysitis (including hypopituitarism and adrenal insufficiency)
 

	Grade 3 or 4	Withhold or permanently discontinue 		
Hyperthyroidism	Grade 2	Continue	
 
Treat with non-selective beta-blockers (eg, propranolol) or thionamides as appropriate
 
	
 
Monitor for signs and symptoms of thyroid disorders.
 

	Grade 3 or 4	Withhold or permanently discontinue 		
Hypothyroidism	Grade 2-4	Continue	
 
Initiate thyroid replacement hormones (eg, levothyroxine or liothyronine) per standard of care
 
	
 
Monitor for signs and symptoms of thyroid disorders.
 

Nephritis and Renal dysfunction	Grade 2	Withhold	
 
Administer corticosteroids (prednisone 1-2 mg/kg or equivalent) followed by taper.
 
	
 
Monitor changes of renal function
 

	Grade 3 or 4	Permanently discontinue		
Myocarditis	Grade 1 or 2	Withhold	
 
Based on severity of AE administer corticosteroids
 
	
 
Ensure adequate evaluation to confirm etiology and/or exclude other causes
 

	Grade 3 or 4	Permanently discontinue		
All other immune-related AEs	Intolerable/persistent Grade 2	Withhold	
 
Based on type and severity of AE administer corticosteroids
 
	
 
Ensure adequate evaluation to confirm etiology and/or exclude other causes
 

	Grade 3	Withhold or discontinue based on the type of event. Events that require discontinuation include and not limited to: Guillain-Barre Syndrome, encephalitis		
	Grade 4 or recurrent Grade 3	Permanently discontinue		

1. Withhold or permanently discontinue pembrolizumab is at the discretion of the investigator or treating physician.
 
NOTE: For participants with Grade 3 or 4 immune-related endocrinopathy where withhold of pembrolizumab is required, pembrolizumab may be resumed when AE resolves to <math>\leq</math> Grade 2 and is controlled with hormonal replacement therapy or achieved metabolic control (in case of T1DM).
				

Dosing interruptions are permitted in the case of medical / surgical events or logistical reasons not related to study therapy (e.g., elective surgery, unrelated medical events, patient vacation, and/or holidays). Subjects should be placed back on study therapy within 3 weeks of the scheduled interruption. The reason for interruption should be documented in the patient's study record.

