#### **7.1.2.4 Vital Signs**

The investigator or qualified designee will take vital signs at screening, prior to the administration of each dose of trial treatment and at treatment discontinuation as specified in the Trial Flow Chart (Section 6.0). Vital signs should include temperature, pulse, respiratory rate, weight and blood pressure. Height will be measured at screening only.

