	Time Course	Did the AE follow in a reasonable temporal sequence from administration of the Merck product? Is the time of onset of the AE compatible with a drug-induced effect (applies to trials with investigational medicinal product)?
	Likely Cause	Is the AE not reasonably explained by another etiology such as underlying disease, other drug(s)/vaccine(s), or other host or environmental factors
Relationship to Merck Product	The following components are to be used to assess the relationship between the test drug and the AE: (continued)	
	Dechallenge	Was the Merck product discontinued or dose/exposure/frequency reduced? If yes, did the AE resolve or improve?

(continued)		
If yes, this is a positive dechallenge. If no, this is a negative dechallenge.          (Note: This criterion is not applicable if: (1) the AE resulted in death or permanent disability; (2) the AE resolved/improved despite continuation of the Merck product; or (3) the trial is a single-dose drug trial); or (4) Merck product(s) is/are only used one time.)

	Rechallenge	
Was the subject re-exposed to the Merck product in this study?          If yes, did the AE recur or worsen?          If yes, this is a positive rechallenge. If no, this is a negative rechallenge.          (Note: This criterion is not applicable if: (1) the initial AE resulted in death or permanent disability, or (2) the trial is a single-dose drug trial); or (3) Merck product(s) is/are used only one time).  NOTE: IF A RECHALLENGE IS PLANNED FOR AN ADVERSE EVENT WHICH WAS SERIOUS AND WHICH MAY HAVE BEEN CAUSED BY THE MERCK PRODUCT, OR IF REEXPOSURE TO THE MERCK PRODUCT POSES ADDITIONAL POTENTIAL SIGNIFICANT RISK TO THE SUBJECT, THEN THE RECHALLENGE MUST BE APPROVED IN ADVANCE BY THE U.S. CLINICAL MONITOR AS PER DOSE MODIFICATION GUIDELINES IN THE PROTOCOL.

	Consistency with Trial Treatment Profile	
Is the clinical/pathological presentation of the AE consistent with previous knowledge regarding the Merck product or drug class pharmacology or toxicology?

The assessment of relationship will be reported on the case report forms /worksheets by an investigator who is a qualified physician according to his/her best clinical judgment, including consideration of the above elements.
		

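### Table 3 holds pembrolizumab for Grade 1 or 2 myocarditis, but its general restart rule lets a Grade 2 event that has settled at Grade 1 be re-dosed

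*Combined protocol and SAP*

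**What the plan says.** Section 5.2.1.2 makes withholding according to Table 3 mandatory. The Myocarditis row withholds at Grade 1 or 2 and discontinues permanently at Grade 3 or 4. Its management cell ties corticosteroid use to severity, and its follow-up cell reads "Ensure adequate evaluation to confirm etiology and/or exclude other causes". The row says nothing about restart.

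Restart is governed by the general instructions at the head of the table. Instruction 1 sets the taper: "Corticosteroid taper should be initiated upon AE improving to Grade 1 or less and continue to taper over at least 4 weeks". Instruction 2 applies wherever drug has been withheld, names no excluded event, and says "pembrolizumab can be resumed after AE has been reduced to Grade 1 or 0 and corticosteroid has been tapered". It then sets an outer limit: "Pembrolizumab should be permanently discontinued if AE does not resolve within 12 weeks of last dose", or if the steroid dose cannot be brought down to the stated level in the same period.

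The only event-specific restart rule in Table 3 is the NOTE on Grade 3 or 4 immune-related endocrinopathy. It permits restart at Grade 2 or below on condition that the event "is controlled with hormonal replacement therapy or achieved metabolic control".

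**The concern.** For myocarditis alone, Table 3 acts at Grade 1. That is a deliberate-looking, stricter threshold for one event, and the general restart rule does not carry it forward. Once a Grade 2 event has come down to Grade 1 and any steroid has been tapered, the restart condition is met at a grade for which the row tells the investigator to hold.

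What is at stake is patient safety and consistent dosing: a patient with unresolved Grade 1 myocarditis may be re-dosed or held, depending on which line of the table the treating investigator follows. No efficacy inference is at stake.

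**Working it through.** The plan states no figure on this point, so the check compares each row's hold grades in Table 3 with the restart range of instruction 2 (Grade 0 or 1).

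| Table 3 row | Grades at which drug may be withheld | Overlap with Grade 0–1 |
|---|---|---|
| Pneumonitis | 2 | none |
| Diarrhea/colitis | 2, 3 | none |
| AST/ALT or bilirubin | 2 | none |
| T1DM/hyperglycemia | 3, 4 (or new-onset T1DM) | none |
| Hypophysitis | 2, 3, 4 | none |
| Hyperthyroidism | 3, 4 | none |
| Nephritis/renal | 2 | none |
| **Myocarditis** | **1, 2** | **Grade 1** |
| All other immune-related | 2 (intolerable or persistent), 3 | none |

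Hypothyroidism is omitted because the drug is continued. Under instruction 2 the overlap occurs in 1 of 9 rows. In the other eight, the lowest hold grade is 2 or 3, so a restart at Grade 1 falls below the trigger, as one would expect.

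**The endocrinopathy NOTE.** It lets Grade 3 or 4 events restart at Grade 2 or below. For hypophysitis, Grade 2 is itself a hold grade, so there is a second overlap. It is written out expressly and comes with a control condition. Myocarditis has neither.

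**Which events are affected.**
- Grade 3 or 4 onset: permanently discontinued, so restart does not arise.
- Grade 2 onset, improved to and remaining at Grade 1: restart permitted by instruction 2, hold grade by the row. This is the conflict.
- Grade 1 onset: unclear. An event that starts at Grade 1 may have to reach Grade 0 before it has been *reduced*.

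**Does the 12-week limit close the gap?** Up to the restart, the last dose is the one before the hold. With steroids, the taper starts at Grade 1 and lasts at least 4 weeks, so even if it must be complete by week 12, any event reaching Grade 1 by week 12 − 4 = 8 can meet the restart condition in time. For example, Grade 1 at week 3 gives an earliest restart at week 3 + 4 = 7. Without steroids there is no taper to wait for. The limit turns on the word *resolve*, which is not defined: if Grade 1 counts as resolved, the limit never applies to this patient; if only Grade 0 counts, the preceding sentence still allows an earlier restart at Grade 1.

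**Do other provisions require Grade 0?**
- Table 6 (Section 7.2.5) requires prior approval of rechallenge after a serious event that the drug may have caused, "OR IF REEXPOSURE TO THE MERCK PRODUCT POSES ADDITIONAL POTENTIAL SIGNIFICANT RISK TO THE SUBJECT". The text continues "THEN THE RECHALLENGE MUST BE APPROVED IN ADVANCE BY THE U.S. CLINICAL MONITOR AS PER DOSE MODIFICATION GUIDELINES IN THE PROTOCOL". It sets no grade and refers back to the guidelines that contain the gap.
- The flow chart marks a directed examination, vital signs and ECOG status at every cycle. Section 7.1.2.4 states that the investigator or designee "will take vital signs at screening, prior to the administration of each dose of trial treatment". Section 7.1.3 has laboratory results reviewed before dosing. None of these sets a myocarditis grade for restart. The ECG is scheduled only at screening (Section 7.1.2.6), and Table 5 lists no troponin or CK.
- The DSMB reviews SAEs (Section 8.1), again without a restart grade.
- The supportive care guidance in Section 5.4.1 has no myocarditis entry.

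**The case against.** The strongest reply is that the two rules answer different questions. The row says when to stop; instruction 2 says when dosing may resume after a hold, improvement and a taper. A treated, evaluated Grade 1 remnant is not the same as a new Grade 1 event, and Table 3 accepts restart at a hold grade for hypophysitis. This is a coherent design. But where the table adopts it, it says so and attaches a condition; for myocarditis it does neither, so intent cannot be read from the text.

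A second reply is that the mandatory, specific row should prevail over a permissive, general sentence. That is a reasonable reading, but the protocol states no order of precedence, and the row is silent on restart. The point that restart is only permitted does stand: a reader might infer that the plan directs re-dosing at Grade 1, and it does not. An investigator who goes on holding breaches nothing.

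A third reply is that safeguards exist, and this also stands in part. Prior approval where re-exposure adds significant risk could well catch a restart into unresolved myocarditis, and the checks at each cycle are real. They reduce the risk without settling which grade permits restart.

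Finally, nothing in the documents establishes Grade 0 as the only acceptable threshold. That is correct, and it is why the fix leaves room for an express Grade 1 rule.

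**Conclusion.** The inconsistency is real and narrow. It concerns Grade 2 myocarditis that improves to Grade 1, persists there, and is considered for restart. In a trial of about 25 patients that path will be rare; the documents give no rate and none is assumed here. The conclusion rests on instruction 2 applying to the Myocarditis row, which its wording supports, and on there being no stated precedence between them.

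Two further inferences are tempting and should not be drawn:
- *That sites will dose differently.* Section 2.1 describes a single-site trial. The possible inconsistency is between investigators.
- *That a definite number of doses could be given to a patient at Grade 1 before week 12.* Any such count depends on whether a restart resets the last dose from which the 12 weeks run, and on what *resolve* means. The text settles neither.

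ORR, the type I error, power and sample size are not affected. The point merits correction because it bears on patient safety and costs one sentence.

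**What to change.** Add to the Myocarditis row of Table 3: *Pembrolizumab may be resumed after Grade 1 or 2 myocarditis only when the event has resolved to Grade 0 and any corticosteroid has been tapered; if it has not resolved to Grade 0 within 12 weeks of the last dose before the hold, permanently discontinue.* This also settles the Grade 1 onset case and, for this row, both undefined terms in the 12-week rule.

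If restart at Grade 1 is intended, the row should say so and state a control condition, as the endocrinopathy NOTE does.

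The cost is one sentence at the next amendment and, in a rare event, a longer hold or an occasional extra discontinuation, possibly in a patient who is responding and has only a mild residual finding. The primary analysis does not change: under Section 9.1, patients with measurable baseline disease who received at least one dose stay in the Full Analysis Set.
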